11.5 Adverse Events of Special Interest

An adverse event of special interest is one of scientific and medical concern specific to the Sponsor's product or program where ongoing monitoring and rapid communication by the PI to the Sponsor may be appropriate. These adverse events may be serious or non-serious. Applicable adverse events may require further investigation in order to characterize and understand, and depending upon the nature of the event, rapid communication by the trial Sponsor to other parties may also be required. These adverse events of special interest must be reported promptly to the sponsor. The adverse events of special interest include the following:

- Local or systemic infection of any origin
- Thrombosis
- Clinically significant decrease in kidney function
- Injection site reactions

If an adverse event of special interest occurs in a study subject, the study subject will be followed for resolution of the adverse event. A decision will be made by the Sponsor concerning further exposure to the study treatment and further participation in the study.

11.6 Unexpected Adverse Events or Unexpected Suspected Adverse Reactions

An AE or suspected adverse reaction is considered “unexpected” if it is not listed in the Investigator’s Brochure (IB) or is not listed at the specificity or severity that has been observed; or is not consistent with the risk information described in the general investigational plan or elsewhere in the current application. For example, under this definition, hepatic necrosis would be unexpected (by virtue of increased severity) if the IB referred only to elevated hepatic enzymes or hepatitis.

The Sponsor will be responsible for reporting any serious and unexpected adverse events to the applicable regulatory agencies as required.

11.7 Treatment and Follow up of Adverse Events

AEs (whether serious or non-serious), including clinically significant abnormal laboratory test values, will be evaluated by the Investigator and treated and/or followed up until the symptoms or value(s) return to baseline or are clinically stable. Treatment of AEs will be performed by appropriately trained medical personnel, either at the clinical site or at a nearby hospital emergency room. When appropriate, medical tests and/or examinations will be performed to document resolution of the event(s).

AEs continuing after completion of the study will be followed up by telephone or with visits per the discretion of the PI. If possible, the outcome of any AE that caused discontinuation from the study or was present at the end of the study should be reported, particularly if the AE was considered by the PI to be related to the study drug.

11.8 Pregnancy

Although pregnancy is not considered an AE, the outcome of a pregnancy, if there is a spontaneous abortion, congenital anomaly or other adverse fetal outcome, may be an SAE. All SAEs are to be reported to the study sponsor on the SAE Reporting Form. Pregnancies will be reported using a pregnancy report form.

WOCBP and males with female partners of child-bearing potential will be instructed to practice an acceptable method of birth control (as defined in [Section 7.1.1](#)) for the duration of the study.

If a female subject or partner of a male subject becomes pregnant during the study, the PI should report the pregnancy to the Safety Monitor within 24 hours of being notified. The subject or partner should be followed by the PI until completion of the pregnancy. At the completion of the pregnancy, the PI will document and report the outcome. If the outcome of the pregnancy meets the criteria for classification as an SAE (i.e. postpartum complication, stillbirth, neonatal death, or congenital anomaly) the PI should follow the procedures for reporting an SAE ([Section 11.4](#)).

12. STATISTICS

12.1 Sample Size Justification

The study will be conducted alongside the ongoing Phase Ib study APL2-CP-PNH-204 (PADDOCK) to investigate APL-2 in PNH patients who have not previously received treatment with eculizumab. Safety and efficacy data from both studies will be used to support the data obtained in the Phase III confirmatory study. Up to 20 subjects will be enrolled to complete 28 days of dosing. The sample size is considered sufficient to obtain useful safety, tolerability, PD and PK data to support the clinical program.

12.2 Statistical Analysis Methodology

A formal Statistical Analysis Plan (SAP) will be developed and finalized prior to locking the database. The full details of data presentations and analyses will be provided therein. Additional statistical analyses other than those described in this section may be performed if deemed

appropriate and included in the SAP. Any deviations from the final analysis plan or from what is outlined in the protocol will be discussed in the final study report.

No formal inferential statistics will be applied to data collected in the study.

The data from this study will also be pooled with the Cohort 2 data from the Phase Ib study APL2-CP-PNH-204 (PADDOCK), which also investigates 270mg/day APL-2 in PNH patients who have not previously received treatment with eculizumab. The details of reporting this pooled data will be documented in a separate SAP.

12.2.1 Analysis Populations

12.2.1.1 Screened Population

The Screened Population will include all subjects who signed the informed consent form and are screened for participation in this study. This set will be used only for the purpose of describing subject disposition.

12.2.1.2 Safety Population/ Intent to Treat (ITT) Population

The Safety Population will include all subjects eligible to receive study medication and who receive at least one dose of study medication. The Intent to Treat Population will be identical to the Safety Population for this study. All baseline characteristics, demographic and efficacy endpoint data will be presented using the ITT Population.

12.2.1.3 Pharmacokinetic (PK) Population

The PK Population will include all subjects in the Safety Population who have at least one quantifiable concentration of APL-2.

12.2.1.4 Pharmacodynamic (PD) Population

The PD Population will include all subjects in the Safety Population who have at least one quantifiable post dose PD parameter.

12.2.1.5 Data Review for Analysis Populations

After all the data have been verified/coded/entered into the database, a review will be performed. The purpose of this review will be to define the analysis populations. The review will also check the quality of the data, identifying outliers, and making decisions on how to deal with problems in any data (e.g., missing values, withdrawals, protocol deviations). After the pre-analysis review, resolution of all issues and documentation of all decisions, the database will be locked.

12.2.2 Study Endpoints

12.2.2.1 Safety Endpoints

The primary safety endpoints of the study are the number and severity of TEAEs. Safety will also be assessed through vital signs, 12-lead ECG and laboratory safety data. Changes from baseline will be calculated using the last measurement prior to the start of dosing as baseline.

12.2.2.2 Efficacy Endpoints

Changes from baseline and percentage changes from baseline in LD, haptoglobin and Hb are the primary efficacy endpoints. They will be calculated for each post dose assessment, where the baseline will be taken as the last measurement prior to the start of dosing.

12.2.2.3 Secondary Endpoints

Secondary endpoints include:

- changes from baseline in FACIT Fatigue Scale (Version 4)
- changes from baseline and percentage changes from baseline in reticulocyte count
- changes from baseline and percentage changes from baseline in total bilirubin
- changes from baseline in the number of RBC transfusions per month and number of units transfused per month
- changes from baseline in LASA scale scores (individual and combined).

Baseline will be taken as the last measurement prior to the start of dosing. For transfusions baseline will be taken from the 12 month transfusion history.

12.2.2.4 Pharmacokinetic Endpoints

Plasma concentrations of APL-2 will be determined from multiple samples taken between Day 1 and the Exit Visit.

12.2.2.5 Exploratory Pharmacodynamic Endpoints (Markers)

Changes from baseline and percentage changes from baseline will be calculated for each of the complement parameters (CH50, AP50 and C3), C3 deposition on RBC cells and clonal distribution of PNH RBCs. Baseline will be taken as the last measurement prior to the start of dosing.

12.2.3 Safety Analyses

All safety endpoints will be evaluated using the Safety Population.

12.2.3.1 Adverse Events

Treatment emergent adverse events (TEAE) are defined as those AEs that develop or worsen after the first dose of study medication and up to 30 days beyond the last dose of study medication. The current version of Medical Dictionary for Regulatory Activities (MedDRA) will be used to classify all AEs.

TEAE will be summarized by system organ class and preferred term. Tabulations will be produced for all TEAEs, for those considered potentially treatment related (causality to study drug is reported as possibly or probably, or where causality is not reported) and for TEAE of special interest. Number of subjects reporting SAEs will also be tabulated.

A by-subject TEAE data listing, including verbatim term, preferred term, treatment, severity, and investigator judgment of relationship to treatment, will be provided.

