11.3.2 Causality

The relationship of an AE to the study drug will be assessed using the following criteria:

Definitely Related	
• Event or laboratory test abnormality, with plausible time relationship to drug intake• Cannot be explained by disease or other drugs• Response to withdrawal plausible (pharmacologically, pathologically)• Event definitive pharmacologically or phenomenologically (i.e. an objective and specific medical disorder or a recognized pharmacological phenomenon)• Rechallenge satisfactory, if necessary
Possibly Related	
• Event or laboratory test abnormality, with reasonable time relationship to drug intake• Could also be explained by disease or other drugs• Information on drug withdrawal may be lacking or unclear
Unlikely Related	
• Event or laboratory test abnormality, with a time to drug intake that makes a relationship improbable (but not impossible)• Disease or other drugs provide plausible explanations
Not Related	
• Event or laboratory test abnormality, is plausibly related to the participant's clinical state, underlying disease, or the study procedure/conditions• Time relationship to drug intake makes a relationship unreasonable• Other obvious causes for event or laboratory test abnormality exist
Unknown	
• Report suggests an adverse event, however, cannot be judged at this time because information is insufficient or contradictory• More data for proper assessment is needed, or additional data is under examination

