### 7.1 Adverse Events

AEs will be coded using MedDRA Version 21.0.

An AE (classified by preferred term) that occurs during the treatment phase will be considered a treatment-emergent AE (TEAE) if it has a start date on or after the first dose of investigational product or if it has a start date before the date of the first dose of investigational product, but increases in severity on or after the date of the first dose of investigational product. If more than one AE with the same preferred term is reported before the date of the first dose of investigational product, then the AE with the greatest severity will be used as the benchmark for comparison to the AEs occurring during the treatment phase under the preferred term. An AE that occurs more than 30 days after the date of the last dose of investigational product will not be counted as a TEAE.

An overall summary of the number of subjects with TEAEs will be presented, including the number and percentage of subjects with any TEAEs, serious TEAEs, TEAEs related to investigational product and TEAEs leading to discontinuation of investigational product.

The number and percentage of subjects reporting TEAEs will be tabulated by system organ class (SOC) and preferred term. TEAEs considered related to investigational product will also be summarized by SOC and preferred term. If more than one AE occurs with the same

preferred term for the same subject, then the subject will be counted only once for that preferred term using the most related occurrence for the summarization by relationship to investigational product.

Summary tables will be presented over the whole study and by study part. AEs will be categorized by the Part in which the AE started i.e. an AE which began during Part 1 will be categorized under Part 1 even if it continues into Part 2A (unless it increases in severity during Part 2A, when it will be counted in both Parts 1 and 2A). Summaries will be ordered by descending order of total events.

All TEAEs will be listed by subject and start date. Separate listings of serious TEAEs and TEAEs leading to discontinuation of study drug will also be generated. The listing will also include duration of AE, the part of the study the AE started and the part of the study the AE stopped.

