#### **13.5.6 Missing Relationship to Investigational Product for Adverse Events**

If the relationship to investigational product is missing for an AE starting on or after the date of the first dose of investigational product, a causality of “Related” will be assigned. The imputed values for relationship to investigational product will be used for incidence summaries, while both the actual and the imputed values will be presented in data listings.

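### The protocol's rule for treatment-related TEAEs names a causality level that its scale lacks and omits Definitely Related, and the SAP does not correct it

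*Protocol*

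**What the plan says.** Protocol 11.3.2 gives the investigator five causality levels: *Definitely Related*, *Possibly Related*, *Unlikely Related*, *Not Related* and *Unknown*. The last is a recorded judgement with its own definition: "Report suggests an adverse event, however, cannot be judged at this time because information is insufficient or contradictory".

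Protocol 12.2.3.1 asks for tabulations of all TEAEs, of TEAEs of special interest, and of "those considered potentially treatment related (causality to study drug is reported as possibly or probably, or where causality is not reported".

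Protocol 12.2 defers to the SAP for detail: "The full details of data presentations and analyses will be provided therein". It adds: "Any deviations from the final analysis plan or from what is outlined in the protocol will be discussed in the final study report".

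SAP 7.1 plans an overall summary with a row for related TEAEs, and a table: "TEAEs considered related to investigational product will also be summarized by SOC and preferred term". A subject with repeated events under one preferred term is counted once, "using the most related occurrence for the summarization by relationship to investigational product". No causality levels are listed.

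SAP 13.5.6 covers missing causality only. It begins "If the relationship to investigational product is missing for an AE starting on or after the date of the first dose" and assigns the value Related. SAP 15 says that only a subset of the protocol analyses is needed after enrolment closed at four subjects. It does not mention the causality rule.

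**The concern.** The rule and the scale do not match. The rule counts a level that nobody can record (Probably) and does not name the level that most clearly belongs there, "Definitely Related". A programmer who applied the protocol text as written would leave out of the related table exactly the events that the investigator was surest about.

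The SAP is where this should have been put right, since the protocol hands the detail to it. The SAP instead uses the word related without saying which levels it covers. A reader who looks for the definition is sent back to the protocol list, which is wrong as written. What is at stake is the numerator of two safety outputs: the related-TEAE row of the overall summary, and the related table by system organ class and preferred term.

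**Working it through.** The plan gives no figure to reproduce, so the check sets the scale beside each rule, level by level.

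| Causality recorded | Protocol 12.2.3.1, read literally | SAP 7.1 with 13.5.6 |
|---|---|---|
| Definitely Related | not counted | not listed; counted on a plain reading |
| Possibly Related | counted | not listed; counted on a plain reading |
| Unlikely Related | not counted | not listed; usually not counted |
| Not Related | not counted | not listed; not counted, by its name |
| Unknown | not counted (it is recorded, so not unreported) | not listed; open |
| Missing | counted | counted (set to Related) |
| Probably | counted, but cannot be recorded | not used |

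Three things follow.

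1. Read literally, the protocol rule counts one of the five recordable levels, and not the strongest.
2. The protocol's silence on a level cannot safely be read as exclusion, because it is also silent on Definitely Related. So it does not settle Unknown either.
3. The SAP maps no level explicitly. How many levels are open depends on how much one is willing to infer. Definitely Related and Not Related follow from their names, and Unknown follows from nothing in the text.

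**Size.** Four subjects were enrolled (SAP 1). In the related-TEAE row, moving one subject changes the percentage by 1/4 = 25 points.

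As an illustration, assume four subjects whose highest causality ratings are Definitely, Possibly, Unknown and Not Related. This pattern is invented; the documents give no ratings.

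- Protocol read literally (Possibly only): 1/4 = 25%.
- SAP on a plain reading, Unknown not counted: 2/4 = 50%.
- SAP on a plain reading, Unknown counted: 3/4 = 75%.
- Any-TEAE row: 4/4 = 100% in every case.

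The step from 25% to 50% is the effect of omitting Definitely Related. The step from 50% to 75% is the effect of leaving Unknown unplaced. If no TEAE is rated Definitely Related or Unknown, all three readings agree and the difference is 0.

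**Does Unknown need a rank for the most-related rule?** Take one subject with an Unlikely Related and an Unknown occurrence of the same preferred term. If Unknown counts as related, the subject is related. If it does not, neither occurrence is. Paired with Definitely or Possibly Related, the subject is related either way. Both SAP outputs are binary, so the related/not-related split decides every case and no separate rank is needed.

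**The case against.** The strongest reply is that the protocol list has no operative effect. The SAP takes over the detail, uses its own wording, and no table in it refers to the protocol's list. Leaving out Definitely Related also contradicts the rule's own label, which starts at a lower level, so this looks like a slip of terminology that no competent programmer would follow. That largely stands. It is why the literal result should not be taken as the expected result. It does not remove the point: the list remains the only level mapping in the two documents, and nothing in the SAP corrects it.

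On Unknown, the protocol describes it as a provisional rating. The pre-lock data review in Protocol 12.2.1.5 could settle leftover cases, and the separate table specifications mentioned in SAP 1 may hold a mapping; they were not available. This also stands. The Unknown gap alone would be missing detail rather than an error.

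A reader might infer three stronger things that the documents do not support:

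- *The primary safety endpoint is under-counted.* It is the number and severity of TEAEs and does not use causality. SAP 7.1 lists all TEAEs by subject, and SAP 13.5.6 shows both actual and imputed relationship in listings, so four subjects can be recounted by hand.
- *The SAP abandons the protocol rule altogether.* SAP 13.5.6 keeps the missing-causality part; only the list of levels is gone.
- *The most-related rule cannot be run without a rank for Unknown.* With binary outputs, it can.

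**Conclusion.** The protocol rule is wrong as written, and the SAP neither replaces it with a correct mapping nor records a correction. The discrepancy itself is certain, because it is a direct comparison of two intact sections. The consequence is minor. It is confined to the related-TEAE row and the related table by system organ class and preferred term, in a descriptive report on four subjects with no formal inference.

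The 25-point step per affected subject is simply one over four, and whether any subject is affected depends on ratings that the documents do not show. The conclusion that the SAP would include Definitely Related events rests on a plain reading of its wording, not on an explicit list. The conclusion on Unknown is limited to the protocol and SAP text.

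**What to change.** In SAP 7.1, replace the protocol's list with a mapping to the actual scale:

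- related: Definitely Related, Possibly Related, or causality missing;
- not related: Unlikely Related or Not Related. Placing Unlikely Related here is a convention that the documents do not dictate;
- Unknown: say on which side it falls. Grouping it with missing is the conservative choice and is in line with SAP 13.5.6, but the documents do not require it.

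Add one line to SAP 15 noting the correction to Protocol 12.2.3.1. SAP 1 allows amendments only before database lock, so if the database is already locked, state the mapping in the study report as a deviation, the route that Protocol 12.2 provides.

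The cost is one or two sentences in SAP 7.1 and one line in SAP 15, with no new data and no new table. The downside is that the related-TEAE count may rise.

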12.2.3.2 Clinical Laboratory Tests

A by-subject listing will be provided including changes from baseline. Laboratory values that are outside the laboratory reference range will be flagged.

12.2.3.3 Vital Signs and ECGs

Observed and change from baseline values for vital sign and ECG parameter will be listed.

Values of potential clinical significance (e.g. change in QTcF \geq 30ms from baseline) will be flagged in listings and summarized.

12.2.4 Efficacy and Secondary Endpoint Analyses

The efficacy and secondary endpoints will be evaluated for the ITT Population.

Absolute values, changes from baseline and percentage changes from baseline (where appropriate) will be summarised, using descriptive statistics, by study visit. Data will be plotted by study day.

The number of RBC transfusions per month and number of units transfused per month will be summarized over the study.

12.2.5 Pharmacokinetic Analyses

The PK concentrations will be evaluated using the PK Population.

Individual concentration over time profile plots will be presented. Median profiles of the concentration-time data, using nominal sampling times, will also be presented. Both linear-linear and linear-log plots will be presented. APL-2 concentrations will be summarized by study visit using descriptive statistics.

Where appropriate, steady-state PK parameters for APL-2 will be estimated from the individual serum concentrations-time data, using actual sample times using a non-compartmental approach. PK parameters will include:

AUC_{total}: The area under the serum concentration versus time curve, from time 0 (pre-dose Day 1) to the last measurable concentration (t) at the end of study.

C_{trough,max}: Maximum observed pre-dose serum concentration.

PK parameters will be summarized using descriptive statistics.

PK data will be combined with the prior data collected in earlier clinical studies and then used to update the APL-2 population PK model (Apellis Data on File).

12.2.6 Pharmacodynamic Analyses

The PD parameters will be evaluated using the PD Population.

Absolute values, changes from baseline and percentage changes from baseline will be summarised, using descriptive statistics, by study visit. Individual parameter over time profile plots will be presented. Median profiles over time, using nominal sampling times, will also be presented.

